11.11.3 INTERIM ANALYSES

One interim analysis is planned for each of the Treatment Naïve and Previously Treated cohorts during the conduct of the study to assess efficacy and safety of U2-V compared with U2 and to allow for release of the results earlier than the planned final analysis in case of significant difference in treatment effect in favor of U2-V.

For the Treatment Naïve cohort, the interim analysis will be performed when approximately 115 PFS events have occurred in both treatment arms combined (67% of the 172 events required for the final primary efficacy analysis). The stopping boundary is based on a Lan-DeMets O'Brien Fleming type spending function. Based on 115 events, the duration of PFS will be tested at the interim analysis, approximately corresponding to a 1-sided p-value of 0.00618 (HR of 0.65). If the number of events is not exactly 115 by the time of the analysis, then the boundary will be updated to reflect the number of events.

For the Previously Treated cohort, the interim analyses will be performed when approximately 82 PFS events have occurred in both treatment arms combined (67% of the 122 events required for the final primary efficacy analysis). The stopping boundary is based on a Lan-DeMets O'Brien Fleming type spending function. Based on 82 events, the duration of PFS will be tested at the interim analysis, approximately corresponding to a 1-sided p-value of 0.00618 (HR of 0.60). If the number of events is not exactly 82 by the time of the analysis, then the boundary will be updated to reflect the number of events.

The DSMB will evaluate efficacy and safety data at the interim analyses and recommend if the study result for each individual cohort should be released early. The same stratification factors as specified in the primary efficacy endpoint analysis will be used. For each of the treatment naïve and previously treated cohorts individually, if the p-value of the stratified 1-sided log-rank test is ≤ 0.00618 for the IRC-assessed PFS analysis and the observed HR is favorable for the U2-V combination treatment, the cohort will have shown statistically significantly longer duration of PFS in the U2-V arm and will have met its primary efficacy endpoint. The results are expected to be presented to the health authorities for potential registrational purposes.

The final primary efficacy analyses for each cohort will be performed when approximately 172 PFS events and 122 PFS events have been observed in the treatment naive and previously treated cohorts,

U2-VEN-207

respectively, where PFS will be tested at the significance level of approximately 0.0462 (two-sided), corresponding to detecting an HR of ≤ 0.74 or less for the treatment naïve cohort and an HR of ≤ 0.70 or less for the previously treated cohort. If necessary, the statistical test level will be adjusted to incorporate the alpha spent at the interim analysis so that the overall type I error rate will be maintained at the 2-sided 0.05 level.

11.11.4 MULTIPLICITY OF PHASE 3 PART

In the efficacy analyses, the following gatekeeping procedures will be implemented to preserve the overall type I error rate across the primary and secondary endpoints of the Phase 3 part of the study at a 2-sided significance level of 0.05.

The type I error control is applied separately to the two cohorts of the study (the treatment naïve cohort and the previously treated cohort) as they are intended to be conducted and analyzed independently and have independent powering.

The primary endpoint PFS analysis will serve as the gatekeeper for the secondary endpoint analyses, i.e., the primary efficacy hypothesis must be rejected before the efficacy hypotheses for the secondary efficacy endpoints can be evaluated.

The secondary endpoints will be sequentially tested at the 2-sided 0.05 significance level in the following order:

- Complete Response (CR) Rate
- Rate of Undetectable Minimal Residual Disease (uMRD)
- Overall Response Rate (ORR)
- Overall Survival (OS)

If a null hypothesis is not rejected, formal sequential testing will be stopped and only nominal significance will be cited for the remaining secondary endpoints. Note, CR Rate, uMRD, and ORR will only be tested once either at the interim or final analysis depending on the outcome of the PFS analysis.

11.11.5 STOPPING RULES

For the Phase 3 portion of the study the following stopping rules will be followed:

- >2 treatment-related Grade 5 events of the same preferred term;
- >5% of enrolled patients discontinuing all therapies due to a treatment-related hematologic toxicity of the same preferred term; OR
- >5% of enrolled patients discontinuing all therapies due to a treatment-related non-hematologic toxicity of the same preferred term.

U2-VEN-207

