4 STUDY DESIGN

4.1 OVERVIEW OF STUDY DESIGN

This is an open-label, multicenter, Phase 2/3 study designed to investigate the efficacy and safety of U2 combined with venetoclax in subjects with CLL/SLL. Patients with treatment naïve and previously treated CLL/SLL are eligible for enrollment. Based on preliminary results from ongoing ublituximab and umbralisib trials and changing landscape of approved CLL/SLL treatments, single-arm or randomized cohorts may be added for both safety and efficacy.

In the Phase 2 stage of the study (see Figure 8 below), 3 separate cohorts will be enrolled: a cohort of approximately 60 subjects with treatment naïve CLL; a cohort of approximately 60 subjects with previously treated CLL, this includes relapsed subjects who are not refractory to a prior BTK inhibitor; and a cohort of approximately 30 subjects with BTK-refractory CLL will be enrolled in the study. BTK-refractory is defined as disease progression while on, or within 6 months of the last dose of, a BTK inhibitor (e.g. ibrutinib, acalabrutinib, etc.). See Section 8 for details on umbralisib administration based on MRD status. As of January 29, 2021, the Phase 2 portion of the study was closed to enrollment.

FIGURE 8: PHASE 2 STUDY DESIGN

BTK-refractory is defined as disease progression while on, or within 6 months of the last dose of a BTK inhibitor (e.g. ibrutinib, acalabrutinib, etc.)

The Phase 3 stage of the trial (Figure 9) includes 2 independent randomized cohorts of CLL/SLL patients; a treatment naïve cohort and a previously treated cohort. Following screening, qualified patients will be randomized 1:1 to 1 of the 2 arms:

- Arm A: Ublituximab + Umbralisib + Venetoclax (U2-V)
- Arm B: Ublituximab + Umbralisib (U2)

U2-VEN-207

[figure not shown]
Approximately 400 (200 per treatment arm) patients will be enrolled to the treatment naïve CLL/SLL cohort and approximately 300 (150 per treatment arm) patients will be enrolled to the previously treated CLL/SLL cohort. The treatment naïve cohort and the previously treated cohorts will enroll independently of each other.

Patients will be randomized and stratified by the following factors:

Treatment Naïve Cohort: 17p status by central lab (deleted or not deleted) and IGHV status (mutated or not mutated)

Previously Treated Cohort: 17p status by central lab (deleted or not deleted) and BTK status (refractory to BTK; yes or no)

FIGURE 9: PHASE 3 STUDY DESIGN

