4.4 STUDY SITES

This study may be conducted in approximately 125 centers. Enrollment is expected to take approximately 24 months.

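### The two >5% safety stopping rules count all Phase 3 enrolled patients together, so an excess confined to U2-V is diluted by the control arm and can reach 10% of Arm A without a trigger

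*Combined protocol and SAP*

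**What the plan says.** Section 11.11.5 opens with "For the Phase 3 portion of the study the following stopping rules will be followed". It then lists three rules: a count rule, ">2 treatment-related Grade 5 events of the same preferred term", and two percentage rules. The first percentage rule is ">5% of enrolled patients discontinuing all therapies due to a treatment-related hematologic toxicity of the same preferred term". The second sets the same limit for toxicity outside the blood system: ">5% of enrolled patients discontinuing all therapies due to a treatment-related non-hematologic toxicity of the same preferred term".

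The section gives no arm, cohort, minimum number, time of evaluation or exposure condition. It also does not say who applies the rules or what is stopped.

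Section 4.1 gives the size of the first cohort: "Approximately 400 (200 per treatment arm) patients will be enrolled to the treatment naïve CLL/SLL cohort". The previously treated cohort is planned at about 300, which is 150 in each arm. In both cohorts, "qualified patients will be randomized 1:1 to 1 of the 2 arms". Section 11.11.4 treats the two cohorts as separate for type I error; Section 11.11.5 makes no such split for safety. Section 13.1 has an independent DSMB review safety about every 6 to 9 months, with power to advise early termination, but does not say how the percentages are to be read. The synopsis mentions a DSMB charter, which is not among the documents.

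**The concern.** The randomised difference between the arms is the addition of venetoclax, so a safety rule in this phase should be able to show a toxicity that appears mainly in U2-V. With 1:1 allocation and a denominator covering everyone enrolled, cases in Arm A are divided by about twice the number of subjects who could have produced them. A nominal 5% limit then acts as a limit of about 10% on Arm A when Arm B contributes no cases. The Grade 5 count rule does not fill the gap, because it covers fatal events only. Non-fatal toxicity that ends all treatment is covered by the percentage rules alone.

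The missing minimum number raises a second question: at very small enrolment, one case already exceeds 5%.

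**Working it through.** **Inputs.** From Section 4.1: 400 + 300 = 700 subjects, 200 + 150 = 350 per arm. From Section 4.4: "Enrollment is expected to take approximately 24 months". From Section 11.11.5: a limit of more than 5%. The documents give no rate of stopping all therapy for one preferred term, so every rate below is an assumption. The public text states no operating characteristic for these rules, so there is no figure of the plan's own to reproduce.

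**Cases needed.** The smallest count that exceeds 5% of n is floor(0.05 × n) + 1.

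| Scope, both arms | n | Cases needed | As a share of Arm A if Arm B has none | Largest Arm A count that does not trip |
|---|---|---|---|---|
| Both cohorts | 700 | 36 | 36/350 = 10.3% | 35/350 = 10.0% |
| Treatment naïve | 400 | 21 | 21/200 = 10.5% | 20/200 = 10.0% |
| Previously treated | 300 | 16 | 16/150 = 10.7% | 15/150 = 10.0% |

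Reading the rule by cohort therefore does not remove the dilution; only reading it by arm does. Within Arm A the same 5% needs 18 of 350 (5.1%).

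**One look at full enrolment** (exact binomial; sum of two binomials where Arm B is not zero).

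| Assumed rate, Arm A / Arm B | Pooled: P(at least 36 of 700) | Arm A only: P(at least 18 of 350) |
|---|---|---|
| 8% / 0% | 7.4% | 98.5% |
| 9% / 0% | 22% | 99.7% |
| 10% / 0% | 46% | >99.9% |
| 8% / 2% | 46% | 98.5% |

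**Checked after every subject.** The plan fixes no evaluation time, so the other extreme is also needed. At 8% / 0% with 1:1 allocation, the average rate per enrolled subject is (8% + 0%)/2 = 4%. An exact recursion over n = 1 to 700 gives the chance that the pooled rule is ever exceeded:
- from the first subject: 0.7845, about 78%;
- from 40 enrolled: 0.6545, about 65%;
- from 175 enrolled (6 months at 700/24 = 29.2 per month): 0.459, about 46%.

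The by-arm reading at 8%, from 40 subjects to 350, gives 99.8%.

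**Early false trips.** 1/19 = 5.26% exceeds 5% and 1/20 = 5.0% does not, so one case is enough up to 19 enrolled. If each event is placed at the moment of enrolment, P(at least one in 19) = 1 − (1 − p)^19:

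| Assumed rate p | First 19 enrolled | Ever, up to 700 |
|---|---|---|
| 0.5% | 9% | 10% |
| 1% | 17% | 19% |
| 2% | 32% | 39% |
| 3% | 44% | 59% |

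These are upper figures, because toxicity and withdrawal of all drugs take time while enrolment continues. Simulating a 2% rate with events spread evenly over 3, 6 or 12 months after entry gives about 6–7%, 2–3% and 1% under uniform accrual. If accrual rises linearly from zero, the figures are about 20%, 10% and 5%. At uniform accrual, 19 subjects are reached in 19/29.2 = 0.65 month.

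**Cost of reading by arm.** At a 2% rate in both arms, with a minimum of 40 and a check after every subject, each arm trips with probability 14.5%. Either arm trips with probability 1 − (1 − 0.145)² = 27%. The pooled rule with the same minimum of 40 trips with probability 14.5%.

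**The case against.** The best reply is that the contrast depends on how the rule is used. The 7% is a single look at 700 with no cases in Arm B. Both arms receive ublituximab and umbralisib, and Arm B continues beyond Cycle 15, so zero is an extreme assumption. With 2% in Arm B the figure is 46%, and with checks after every subject the 8% / 0% case reaches about 78%. This stands, and a reader should not infer that the pooled rule is nearly blind to an Arm A signal. Part of that 78% comes from very small denominators, however, and from 175 enrolled it is 46%. The count at full enrolment does not depend on any assumed rate.

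A reader might also infer that the rule will probably stop the trial falsely at the start. The documents do not support this. The 32% and 39% figures put toxicity at the moment of enrolment, and the one-case window lasts under a month at uniform accrual. By the summary of amendments, the stopping rules came in with Version 4.0 (October 2021), after Version 3.0 (January 2021) had added Phase 3, so the window may already have passed.

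Pooling is the natural reading rather than a stated one, and the charter may define the denominator. The DSMB can also advise stopping on its own judgement. Both points lower the stakes. Neither changes the text of a rule that the protocol says will be followed and that does not defer to the charter. The documents do not say whether the DSMB receives counts by arm, so nothing here rests on that either way.

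**Conclusion.** The concern holds as a point about the denominator. On the plain reading, the percentage rules allow up to 10.0% of Arm A to stop all therapy for one preferred term, with none in Arm B, before they act at full enrolment. The loss of sensitivity is large at a single late look (7% to 46% across the assumed scenarios, against at least 98.5% by arm). It is moderate under continuous checking (about 78%, or 65% from 40 enrolled, against 99.8% by arm from 40). All probabilities rest on assumed rates and on one preferred term at a time.

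The missing minimum number is secondary. At an assumed 2% rate the false-trip chance is roughly 1–7% under uniform accrual once time to toxicity is allowed for, with 39% as an upper figure. The 5% value itself is not in question. This is a cheap improvement, not a flaw that undermines the trial.

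**What to change.** Keep the sponsor's 5%. State in Section 11.11.5 that it is read within each randomised arm, with subjects who received at least one dose as the denominator, from a minimum number chosen by the sponsor and the DSMB. Cases before that number go to individual review. State also whether the cohorts are read separately, when the rule is evaluated, who applies it and what a trigger leads to. Record the resulting trigger probabilities in the DSMB charter over a range of rates.

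The work is protocol and charter wording. The statistical price should be disclosed: at the same minimum, two arms give two chances of a false trigger (about 27% against 14.5% in the example with a minimum of 40 and a 2% rate; 40 is only an illustration). A larger minimum, or evaluation only at DSMB meetings, would lower this. The percentage rule would also be inactive for the first subjects in each arm, which is why early cases need individual review.

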1.6 RATIONALE/HYPOTHESIS FOR U2 + VENETOCLAX COMBINATIONS

While venetoclax therapy is highly active in patients with CLL/SLL, relapses occur. Additionally, the majority of patients only achieve a PRs to currently available venetoclax combinations. Further, a practical limitation exists with the TLS risk mitigation strategy required for venetoclax administration, which requires intensive monitoring for patients at medium and high risk of TLS and makes administration challenging in the community setting. We hypothesize that the addition of venetoclax following U2 induction will provide deeper levels of remission than have been achieved with single-agent umbralisib, ublituximab, and venetoclax to date. Further, the sequential strategy has been designed to mitigate the risk of venetoclax related TLS by utilizing a debulking course of U2 prior to initiation of venetoclax. Lastly, sequential monitoring for rate of undetectable MRD will be used to potentially inform future time limited therapies based on the achievement of early optimal response.

Based on the above, we propose this Phase 2/3 trial to evaluate U2 with venetoclax (U2-V) and also to compare the U2 regimen in a randomized fashion to the triplet regimen of U2-V.

The combination of U2-V has been evaluated in an ongoing Phase 1 study (NCT03379051) in patients with relapsed or refractory CLL, which supports the dosing regimen used in this study U2-VEN-207. Of 43 patients treated to date, Grade ≥ 3 AEs were infrequent with neutropenia (21%), leukopenia (12%), and IRRs (7%) occurring in over 5% of patients (Barr et al., 2020). Discontinuations due to AEs were also uncommon with 9% and 4% discontinuing umbralisib and venetoclax respectively. No DLTs were observed during the Phase 1 portion, and the RP2D was found to be umbralisib 800 mg QD, ublituximab 900 mg, and venetoclax at standard dosing. The Phase 1 study utilized a 3 Cycle debulking schedule for U2, similar to this Protocol U2-VEN-207. After 3 cycles of U2 debulking, there was an 81% relative reduction in high- and medium-risk TLS, and no patients developed clinical or laboratory TLS during venetoclax administration. Of 27 patients evaluable at Cycle 12, the triple combination of U2 plus venetoclax produced a 100% ORR, 41% CR, and high rates of uMRD in the peripheral blood (96%) and BM (77%). The findings of the Phase 1 study support continued investigation in the current trial.

U2-VEN-207

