8.5.2.2 DOSE HOLD/MODIFICATION: UMBRALISIB

Supportive care should be considered for any subject who experiences $Grade \ge 2$ cytopenias, or $Grade \ge 1$ non-hematologic toxicities. If a subject experiences a treatment-related AE requiring dose modification during the course of therapy, then study drug administration should be held, as necessary, until the AE resolves or stabilizes to an acceptable degree. In addition, the subject should be notified of the change in dose and the appropriate clinic staff should instruct the subject about the revised number of study medication tablets to be used per dose according to the new dose level. Any questions regarding dose modification should be referred to TG Therapeutics.

The adjunctive supportive care recommendations listed in the dosing hold and modification tables are meant to serve as guidelines and are not meant to replace Investigator discretion. Final toxicity

U2-VEN-207

management decisions are the responsibility of the clinical Investigator. However, adherence to study drug dose hold, dose reduction, and dose discontinuation criteria are strongly advised for patient safety reasons. Please contact the Sponsor with any questions related to managing side effects, holding treatment or other dose modifications. If a subject discontinues only one study drug, the subject may continue treatment with the other study drug(s) per the protocol. Please see Table 22 for further guidance.

TABLE 18. STUDY DRUG DOSE REDUCTION RECOMMENDATIONS

Study Drug	Starting Dose	1st Dose Reduction	2 nd Dose Reduction
Umbralisib	800 mg	600 mg	400 mg

A maximum of 2 dose level reductions are allowed for umbralisib.

If a subject requires a dose reduction of umbralisib due to study drug-related AE, the dose may not be re-escalated. If further evaluation of the toxicity reveals the AE was not related to umbralisib, this must be recorded in the medical record and dose re-escalation to the next higher dose level may be considered at the discretion of the Investigator.

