8.5.4 DOSE HOLD/MODIFICATION: UBLITUXIMAB, UMBRALISIB AND VENETOCLAX

Table 22 illustrates the dose hold and modifications for all investigational products in the present study.

Subjects should be assessed clinically for toxicity at each visit using the NCI CTCAE v5.0 (https://ctep.cancer.gov/protocoldevelopment/electronic_applications/docs/ctcae_v5_quick_reference_5x7.pdf) grading scale.

Dose hold and/or modification guidance is for adverse events considered *related* to the study drug(s). If the adverse event is *not considered related* to a study drug (ublituximab, umbralisib and/or venetoclax), then that drug does not need to be modified or held as per Investigator assessment.

If cytopenias are deemed related to the underlying disease rather than study drug, dose modifications are not required, or are per investigator discretion. If a subject discontinues one or more study drugs, the subject may continue treatment with the other study drug(s) per the protocol.

U2-VEN-207

Dose reduction and/or holds are permitted as per Investigator discretion to manage adverse events related to one or more of the study drugs. The guidelines below are recommendations and are not meant to replace Investigator discretion.

TABLE 22. STUDY DRUG MODIFICATIONS

	Ublituximab	Umbralisib	Venetoclax	
NCI CTCAE Grade				
Neutropenia				
Grade 1-2 neutropenia	Maintain full dose. Consider growth- factor support as warranted.	Maintain current dose. Consider growth-factor support as warranted.	Maintain current dose. Consider growth-factor support as warranted.	
Grade 3 neutropenia	Maintain full dose. For recurrent or persistent Grade 3 neutropenia hold ublituximab until Grade ≤2, then resume. Consider growth- factor support as warranted.	Maintain current dose. If recurrence or persistent Grade 3, hold umbralisib until Grade ≤ 2 and resume at same dose. Consider growth-factor support as warranted.	Maintain current dose, if Grade 3 recurs or is persistent then hold venetoclax until ≤ Grade 2, after resume at the same dose. Consider growth-factor support as warranted.	

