РЈР	For suspected, PJP, withhold ublituximab until evaluated. Provide supportive care, once resolved resume at full dose.	For suspected, PJP, withhold umbralisib until evaluated. Provide supportive care, once resolved resume at same dose.	For suspected, PJP, withhold venetoclax until evaluated. Provide supportive care, once resolved resume at same dose.	
CMV infection or viremia	Withhold ublituximab, until infection or viremia resolves, provide supportive anti- viral therapy as warranted, then resume at full dose.	Withhold umbralisib, until infection or viremia resolves, provide supportive antiviral therapy as warranted, then resume at same or reduced dose.	Withhold venetoclax, until infection or viremia resolves, provide supportive anti- viral therapy as warranted, then resume at same or reduced dose.	

U2-VEN-207

Diarrhea / Colitis			
	Ublituximab	Umbralisib	Venetoclax
		Maintain current dose of umbralisib, if tolerable, or hold and then resume at current dose level once has resolved. Consider supportive care.	
Grade 2 diarrhea	Maintain full dose.	NOTE: If persistent Grade 2 diarrhea, despite supportive care, hold umbralisib until ≤ Grade 1. If recurrence after rechallenge, hold umbralisib until ≤ Grade 1; thereafter resume at current dose or next lower dose level at discretion of the Investigator.	Refer to venetoclax prescribing information.
Grade ≥ 3 diarrhea	Maintain full dose.	Administer supportive care. Hold umbralisib until Grade ≤2; thereafter, resume umbralisib at reduced dose. If severe diarrhea recurrence after rechallenge discontinue umbralisib.	Refer to venetoclax prescribing information.
Grade ≤ 2 colitis	Maintain full dose.	Hold umbralisib. Treat with supportive care and after resolution of colitis, resume umbralisib at same or next lower dose level.	Refer to venetoclax prescribing information.
Grade 3 or 4 colitis	Maintain full dose.	Hold umbralisib. Treat with supportive care and after resolution of colitis, resume umbralisib at next lower dose level. If recurrence after dose	Refer to venetoclax prescribing information.

U2-VEN-207 Dated: 05 October 2021 (Ver 4.0)

Grade 1 Maintain full dose. Maintain current dose. Assess Concomitant Medications and Risk Factors*. Monitor Labs every 1-2 weeks. Maintain current dose. Assess Concomitant	r to venetoclax cribing information.

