Grade 1 Maintain full dose. Maintain current dose. Assess Concomitant Medications and Risk Factors*. Monitor Labs every 1-2 weeks. Maintain current dose. Assess Concomitant	r to venetoclax
Grade 1 Maintain full dose. Assess Concomitant Medications and Risk Factors*. Monitor Labs every 1-2 weeks. Maintain current dose. Assess Concomitant	
Assess Concomitant	
Crade 2 Maintain full doco discretion T	r to venetoclax cribing information.
If liver toxicity recurs to Grade 2 once off steroids, re-initiate steroids and consider withholding umbralisib.	
Crade > 3	r to venetoclax cribing information.

U2-VEN-207

Investigator discretion)**.	
Monitor labs at least weekly until Grade 1.	
Once resolved to Grade ≤1, taper prednisone. Resume umbralisib at next lower dose level when Grade ≤1.	

^{*}Assess for disorders of lipids and glucose, thyroid disorders, alcohol use, viral infections, etc.

Important: Before initiating steroids, check for viral hepatitis or CMV infection.

If Grade 4 anaphylaxis is observed at any point during ublituximab treatment, permanently discontinue ublituximab treatment and intervene as per Investigator discretion.

If a subject requires a dose reduction of umbralisib due to study drug-related toxicity, the dose may not be re-escalated. If further evaluation of the toxicity reveals the event was not related to umbralisib, this must be recorded in the medical record and dose re-escalation to the next higher dose level may be considered at the discretion of the Investigator.

Supportive care should be considered for any subject who experiences $Grade \ge 2$ cytopenias, or $Grade \ge 1$ non-hematologic toxicities. If a subject experiences a treatment-related AE requiring dose modification during the course of therapy, then study drug administration should be held, as necessary, until the AE resolves or stabilizes to an acceptable degree.

U2-VEN-207

^{**}Supportive Care – Aggressive management of lipid, glucose, other metabolic disorders, viral infections, etc.

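### Both >5% stopping rules in section 11.11.5 count only subjects who stop every drug, so they are insensitive to toxicity managed by stopping one drug

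*Combined protocol and SAP*

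**What the plan says.** Section 11.11.5 lists three rules for Phase 3. The first is ">2 treatment-related Grade 5 events of the same preferred term". The other two depend on discontinuation: ">5% of enrolled patients discontinuing all therapies due to a treatment-related hematologic toxicity of the same preferred term" and ">5% of enrolled patients discontinuing all therapies due to a treatment-related non-hematologic toxicity of the same preferred term". In both, a subject enters the count only when every drug has been stopped for the same term.

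The dosing sections work drug by drug. Section 8.5.2.2 says "If a subject discontinues only one study drug, the subject may continue treatment with the other study drug(s) per the protocol", section 8.5.3.3 repeats this for venetoclax, and section 8.5.4 says "If a subject discontinues one or more study drugs, the subject may continue treatment with the other study drug(s) per the protocol". In Table 22, the row for Grade 3 or higher diarrhea says of umbralisib: "If severe diarrhea recurrence after rechallenge discontinue umbralisib". In the same row ublituximab stays at full dose and venetoclax is left to its prescribing information. The legible Grade 2 liver text also acts on umbralisib: "re-initiate steroids and consider withholding umbralisib".

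On observed rates, section 1.6 reports from an earlier U2-V study of 43 patients: "Discontinuations due to AEs were also uncommon with 9% and 4% discontinuing umbralisib and venetoclax respectively". It gives no rate for stopping all drugs.

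**The concern.** A site that follows the recurrent severe diarrhea row stops umbralisib for good and adds nothing to the count for the non-hematologic rule. Section 1.3 names severe diarrhea/colitis and liver toxicity among the autoimmune-related toxicities on which umbralisib is compared with other drugs of its class, so the gap falls on events that the protocol itself highlights. The share of subjects permanently losing one drug for one term could pass 5% without either rule registering it.

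The count is also uneven between arms. From Cycle 4, stopping all therapy means stopping three drugs in Arm A but two in Arm B, so the same toxicity handled in the same way is harder to count in the experimental arm.

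**Working it through.** The documents give no operating characteristic for these rules, so there is no stated figure to reproduce.

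**Inputs**
- Threshold: more than 5% of enrolled subjects, all therapies stopped, one preferred term (11.11.5).
- u, the umbralisib discontinuation rate: 9% (1.6). It covers all AEs and all terms, so it is generous as a rate for related events under one term. It is consistent with 4/43 = 9.3%, exact 95% CI 2.6% to 22.1%.
- N: 400 and 300 per cohort, 200 and 150 per arm, 700 in all (4.1). Section 11.11.5 does not say which of these is the denominator.
- f, the share of umbralisib stops that become all-drug stops: not in the documents. Assumed range 25% to 100%.
- s, the share of stops under one preferred term: not in the documents. Assumed 1 (upper bound) and 0.5.

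**Step 1, stops needed.** r = floor(0.05 × N) + 1, which gives 36 of 700, 21 of 400, 16 of 300, 11 of 200 and 8 of 150.

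**Step 2, break-even share.** The expected all-drug rate is u × s × f, so f must exceed 0.05/(u × s).
- s = 1: 0.05/0.09 = 0.556, so more than 56% of stops (rounded) must be all-drug stops.
- s = 0.5: 0.05/0.045 = 1.11. The expected rate stays below 5% even if every stop is an all-drug stop.

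**Step 3, probability of tripping.** P = Pr{Binomial(N, u × s × f) ≥ r}, one look at full N, u = 9%, the same rate in both arms where arms are pooled:

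| f | s = 1, N = 400 | s = 1, N = 150 | s = 0.5, N = 400 | s = 0.5, N = 150 |
|---|---|---|---|---|
| 25% | 0.000 | 0.021 | 0.000 | 0.000 |
| 50% | 0.27 | 0.36 | 0.000 | 0.021 |
| 75% | 0.91 | 0.80 | 0.03 | 0.14 |
| 100% | 0.998 | 0.965 | 0.27 | 0.36 |

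**Step 4, sensitivity to u.** At u = 22%, near the upper confidence limit, with s = 1, the break-even share is 0.05/0.22 = 23%. A 25% share then trips with probability 0.62 (N = 400) or 0.59 (N = 150).

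**Step 5, a single-drug count at the same 5% level.** With a true rate of 9% under one term, P is 0.998, 0.993, 0.975 and 0.965 for N = 400, 300, 200 and 150. With a true rate of 4.5% it is 0.27, 0.28, 0.29 and 0.36.

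**The case against.** A limit on intolerance of the whole regimen is a coherent choice, and section 11.11.5 does not say that the rules are meant for single-drug toxicity. Continuing the other drugs is allowed, not required. Table 22 is guidance subject to investigator discretion, and section 4.5 expressly foresees stopping all drugs for intolerable toxicity. The Grade 5 rule does not depend on discontinuation. Under section 13.1 the DSMB reviews safety about every 6 to 9 months and may advise termination.

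Much of this stands, and it limits what can be said. A reader might infer that the rules can almost never trip, or cannot detect the toxicities of interest. The documents do not support that: the result turns on f, which they do not give, and at a high f or a high stop rate the rules do fire. A reader might also take the 4% venetoclax figure in section 1.6 as a ceiling on all-drug stops. It is not one. That study gave three cycles of U2 before venetoclax, so a patient could stop everything without ever discontinuing venetoclax. Nor is 4% a whole count of 43 (1/43 = 2.3%, 2/43 = 4.7%), so its denominator is unclear.

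Nor does Table 22 stop drugs singly throughout. For Grade 4 neutropenia, Grade 4 thrombocytopenia and Grade 3 or 4 infection all three drugs are held together, though only temporarily. Parts of the colitis and liver rows are broken in the text available, and nothing is drawn from the missing cells.

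The backstops do not close the gap. The Grade 5 rule needs deaths. At 700 subjects in 24 months (about 29 a month, uniform accrual assumed), roughly 175 to 262 subjects enroll between DSMB meetings.

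**Conclusion.** The point holds as a statement about what is counted. Both >5% rules are insensitive to toxicity managed by stopping one drug, and they require more drugs to be stopped in Arm A than in Arm B. At a 9% umbralisib stop rate, all under one term, the expected rate exceeds 5% only if more than 56% of stops are all-drug stops. With 400 enrolled, the probability of tripping runs from about 0.00 to 0.998 as that share goes from 25% to 100%.

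These figures assume that the rate in the earlier study carries over to Phase 3, that there is one look at full enrollment, and that f and s lie in the ranges shown. Repeated checking would raise all the probabilities. The DSMB and the Grade 5 rule remain in place, so this is a cheap improvement to safety monitoring and not a failure of it.

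**What to change.** Reconcile section 11.11.5 with 8.5.2.2, 8.5.3.3 and 8.5.4. Keep the two all-therapy rules as they are. Add to 11.11.5 and the DSMB charter a monitoring count of permanent treatment-related discontinuation of each study drug, separately for ublituximab, umbralisib and venetoclax, by preferred term. Crossing >5% for any drug and term triggers an unscheduled DSMB review, not an automatic stop. State the denominator of the count and its operating characteristics.

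Confirm that the eCRF records the drug and the reason for each permanent discontinuation. Sections 11.4 and 11.9 refer to reasons for discontinuing study treatment, which section 4.5 defines as all drugs, and 11.7 covers dose modifications, so collection by drug is not expressly shown.

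No patient-level dose rule changes. The cost is a short addition to two documents and an occasional extra DSMB review. Some reviews will be called when the true rate is just under 5%: at a true 4.5% under one term, the probability is about 0.27 to 0.36 for the cohort and arm sizes above.
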